We will also consider in a sensitivity analysis the role of Triple P practitioner as an additional source of clustering. As practitioners will deliver the intervention to several families allocated to the intervention arm only, this will be a form of partial nesting and may lead to an underestimation of standard errors (and thus inflated Type-I error) if not appropriately accounted for. To account for any clustering, we will fit a heteroscedastic partially nested mixed-effects model. We will also report intra-cluster correlation coefficients, the number of clusters, and cluster sizes.

Secondary outcomes will be analysed similarly. However, secondary outcomes that are adolescent self-report will use linear regression to compare mean scores between trial arms, controlling for baseline scores, age, sex, and local authority. No random effects are included when analysing these outcomes as we do not need to adjust for parent clustering of responses, i.e. there is no dependency of responses from within the same household as we only anticipate one adolescent per household to respond.

We will explore the extent to which there were differential intervention effects by local authority by extending our primary analysis model to include sub-group by trial arm interaction

terms. Similarly, potential moderators, young person learning disability status, ethnicity, and in-care vs in family home status, will be explored by inclusion of an interaction of moderator and treatment allocation variables into the primary analysis model. In addition to interpreting the magnitude and statistical significance of interactions, plots of the interactions will also be examined. These analyses will be hypothesis generating in nature only (i.e., will not be confirmatory and only indicate whether further research targeting the intervention may be warranted).

We will conduct two further sensitivity analyses:

- Exploring the impact of missing data on trial outcomes by investigating likely missing data mechanisms and re-fitting the primary outcome within a multiple imputation framework (including exploring MAR and MNAR mechanisms via delta-based controlled multiple imputation);

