2. Generate evidence to consider whether TEEN TRIPLE P + SAU, (a) reduces parent reported adolescent internalising behaviour and increases prosocial behaviours at 6 months and 12 months post-randomisation, and (b) reduces adolescent reported externalising and internalising behaviour problems and increases prosocial behaviours at 6 and 12 months post-randomisation, (c) improves parenting practices, parent self-regulation, interparental relationships, parental-adolescent relationships and parental well-being at 6 and 12 months post-randomisation, decreases adolescent parent reported antisocial behaviours at 12 months post-randomisation, and (d) reduces the chance of a child going into out of home placement over a 12 month period.
3. Carry out exploratory sub-group analyses of outcomes by adolescent learning disability status and whether living with foster versus biological/adoptive parents.
4. Assess the sensitivity of findings under different assumptions with respect to missing data.
5. Monitor and report and adverse events related to TEEN TRIPLE P.
6. Complete a process evaluation using key indicators drawn from the logic model, including an evaluation of acceptability and the experiences of parents/carers, adolescents with a broad range of ethnic and diverse backgrounds, and other key stakeholders (e.g., practitioners, delivery team), and fidelity of delivery of TEEN TRIPLE P.
7. Monitor and report adverse events related to TEEN TRIPLE P.

Study Materials

Trial design

A two-arm cluster (with families as the clusters) randomised efficacy RCT of Standard Teen Triple P (TEEN TRIPLE P) plus SAU vs. SAU alone, running over 40 months, involving parents and foster carers of young people aged 11-15 years on the edge-of-care. There will be 6- and 12-month follow-ups, and a process evaluation and internal pilot. 412 Parent/Carer and their Young person(s) at the edge of care will be recruited. Families will be randomised on a 1:1 basis to either intervention or control arm using stratified permuted block randomisation, stratifying by local authority. Clustering by family unit accounts for the dependency between the observations from the same family (i.e. both parents can respond as both parents can take part in the study if they choose). This approach has been routinely used in practice (Coulman et al., 2020; Bell et al. 2008).

Trial design, including number of arms		Two-arm cluster randomised control trial
Unit of randomisation		Families

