	measure (instrument, scale, source)	Parent completed Strengths and Difficulties Questionnaire (SDQ) – externalising scale (SDQ; Goodman, 1999) at baseline
Baseline for secondary outcome	variable	(1) Parent reported - Adolescent behavioural and emotional problems (2) Parenting practices (3) Parent and Adolescent reported prosocial behaviours (4) Adolescent reported peer relationships (5) Interparental outcome (6) Parent mental health (7) Parent Wellbeing (8) Conflict Behavior (9) Child-parent relationship (10) Family functioning (11) Parent self-regulation – the Parenting Self-Regulation (12) Out of home placement 
 • Adolescent antisocial behaviours
	measure (instrument, scale, source)	(1) Strengths and Difficulties Questionnaire (SDQ; Goodman, 1999) parent report internalising problems scale, adolescent report externalising and internalising problems scales at 6 and 12 months. (2) Parenting practices: Parenting Scale Adolescent version (PSA) parent report (3) Adolescent prosocial behaviours – The Prosocial behaviour subscale of the SDQ (Goodman, 1999). Adolescents and parents report at 6 and 12 months.

		
(4) Adolescent peer relationships – The Peer Relationship Problem subscale of the SDQ (Goodman, 1999)
 
(5) Interparental outcome - Dyadic Adjustment Scale (DAS-7) is a 7-item measure (Sharpley & Cross 182; Hunsley et al., 2001)
 
(6) Parent mental health – the Kessler 6 (Kessler et al., 2003)
 
(7) Parent Wellbeing - The Warwick-Edinburgh Mental Well-being Scale (SWEMWBS; Tennant et al., 2007)
 
(8) Conflict Behavior Questionnaire (CBQ-20) (Robin & Foster, 1989)
 
(9) Child-parent relationship – the Closeness subscale of the Child-Parent Relationship Scale (CPRS, short form) measures (Pianta, 1995)
 
(10) Family functioning – the Family APGAR scale (Adaptability, Partnership, Growth, Affection and Resolve; APGAR; Smilkstein, 1978).
 
(11) Parent self-regulation – the Parenting Self-Regulation Scale is a 12-item parent-completed measure of parental-regulation (Tellegen et al., 2022).
 
(12) Out of home placement
 
(13) Adolescent antisocial behaviours - Self Report Delinquency Measure (SRDM; Smith & McVie, 2003)

--	--	---

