All participants (in both trial arms) will complete assessments at baseline (prior to randomisation), 6- and 12-months post-randomisation and will be given a choice of how these are completed. These assessments can be completed in a number of ways, face-to-face, online on a website, via telephone, via videoconferencing, or on paper via the post. Participants, parents/guardians, young people and key stakeholders will be invited to participate in semi-structured interviews to ascertain acceptability and their experience of

the parenting programme and being in the trial. We will interview a sample of those randomised to each arm of the trial.

Randomisation

Families will be randomised with equal probability to either the intervention or comparator arm using random permuted blocks (block size 4), stratified by local authority site. The statistician doing the analysis will be blind to the treatment allocation. As the families and practitioners are not blind to treatment allocation (as this would be impossible given the intervention), there is no issue in terms of predictability.

Sample size

Sample size calculations were conducted using R version 4.1.2 (2021-11-01), and the 'pwr' R package.

Parents/carers within the same family will be randomised to the same arm, making this a cluster RCT, given responses within the same family are potentially highly correlated. We might expect, based on our previous research with families and consultation with the TMG (Trial Management Group), an average cluster size within families of up to a maximum of 1.5 parents and a high degree of correlation among parents/carers from the same family, so also allow for an ICC=0.5 (Davé et al., 2008). Following Teerenstra et al. (2012), we also allow for a correlation between baseline and follow-up measures of primary outcome of $r=0.5$ (this is a conservative estimate based on published SDQ test-retest correlations between 0.74-0.84; Nowak et al., 2008). The sample size is then inflated to account for 20% of families being lost to follow-up at the 12-month post-randomisation follow-up time point.

Allowing for the above assumptions and an effect size to be detected of 0.35 with 90% power and a two-sided alpha of 0.05, a sample size of $N=412$ ($N_1=206$, $N_2=206$) is required.

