- Delinquency – the Self Report Delinquency Measure: Baseline and 12 month follow up data will be collected. Baseline and 12-month follow up data will only be used in the 12 month followup addendum report. The SRDM is a derived total score following Smith & McVie (2003) and the units are a relative measure of delinquency. The SDRM is a measure comprising 15-items pertaining to antisocial behaviours (e.g., burglary, violence). It requires CYP to respond with yes or no with reference to a time-period (6 months). They then report the estimated frequency of the behaviour, and whether they have ever been caught. Each items frequency is scored 0-5, 6-10 is scored 6 and 11+ is scored 11. Minimum score would be 0 and maximum number of delinquent behaviours would be 165 (15x11). On this basis, we are likely to have a skewed continuous distribution, so some transformation may be required after inspection of model residuals. In addition, there may be a number of individuals where this is their first time in a custody unit, so there is a possibility of floor effects depending on the

frequency of their delinquent behaviour. A higher number of delinquent behaviours is bad, so a reduction in the outcome indicates an effective treatment.

Analysis methods

List of methods and presentation

Internal pilot study

Statistical analysis for internal pilot feasibility outcomes will be primarily descriptive. Feasibility outcomes (primary outcome measures and all secondary measures) will be estimated as frequencies and percentages, means and standard deviations, or medians and interquartile ranges as appropriate. Feasibility outcomes will be assessed against the pre-specified progression criteria.

Primary analysis (6 month)

Our primary analysis will include all randomised participants who provide outcome data (i.e., a intention to treat basis) and compare mean scores between arms on the SDQ externalising behaviour at 6-months post-randomisation using a linear mixed model, adjusting for baseline SDQ score and local authority. A random intercept will also be included to account for family level clustering at level 2 (individual at level 1 and family at level 2).

$$L1: Y_{ik} = \beta_{0k} + \beta_{1k}SDQ_BL_{ik} + \beta_{2k}local_authority_{ik} + r_{ik}, \quad r_{ik} \sim N(0, \sigma^2)$$

$$L2: \beta_{0k} = \gamma_{00} + \gamma_{20}TX_k + \mu_{0k}, \quad \mu_{0k} \sim N(0, \tau_2^2)$$

$$\beta_{1k} = \gamma_{10}$$

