where, Y_{ik} are the SDQ scores; SDQ_BL_{ik} are the baseline SDQ scores; TX_{ik} is the treatment/control variable indicator; $Local_authority_{ik}$ are indicator of local authority (strata, 6 groups: Cambridge, Peterborough, Wirral, Birmingham, London Borough Merton, Gloucestershire); μ_{0k} is the random intercept term for family and r_{ik} is the individual level variation.

We will use simple coding for the contrast of local authority, so that our intercept retains the grand mean and nominally use Birmingham as our reference level.

Distributional assumptions for the primary linear model will be checked and alternative methods are listed in section “assumption checking”.

If insufficient random effect variance is found, we will reduce the model to a linear regression with cluster robust standard errors (Green & Vavreck, 2008). The alternative primary analysis would be specified as follows:

$$Y_i = \beta_0 + \beta_1 SDQ_BL_i + \beta_2 local_authority_i + \beta_3 TX_i + r_i, \quad r_i \sim N(0, \sigma^2)$$

Secondary outcomes analysis

Secondary outcomes will be analysed following the same method as the primary outcome. However, the distributions of these secondary outcomes will be assessed prior to conducting the analysis, if range restriction is present or a binary outcome (out of home placement), we will consider using a generalized linear mixed model (GLMM) instead (Poisson or logistic respectively). All measures have scores that are integer numbers and positive scores, so the Poisson distribution under this condition is completely acceptable if needed. The GLMM is denoted as follows:

$$L1: g(Y_{ik}) = \beta_{0k} + \beta_{1k} SDQ_BL_{ik} + \beta_{2k} local_authority_{ik} + r_{ik}, \quad r_{ik} \sim N(0, \sigma^2)$$

$$L2: \beta_{0k} = \gamma_{00} + \gamma_{02} TX_k + \mu_{0k}, \quad \mu_{0k} \sim N(0, \tau_2^2)$$

$$\beta_{1k} = \gamma_{10}$$

Note: $g(.) = \log_e(.)$, where $g(.)$ is the log link function for the secondary outcome measures for example, if a count model was more appropriate for the scores, whereas the primary outcome, $g(Y_i) = Y_i$.

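### The SAP's secondary-outcome model carries baseline SDQ as its only baseline score, so the non-SDQ scales are not adjusted for their own collected baselines

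*SAP*

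**What the plan says.** SAP, Secondary outcomes analysis: "Secondary outcomes will be analysed following the same method as the primary outcome". SAP, Primary analysis (6 month), defines that method as a linear mixed model with a family random intercept, "adjusting for baseline SDQ score and local authority". The generalised mixed model printed for secondary outcomes has the same right-hand side. Its only baseline score is SDQ_BL, which the SAP defines once, under the primary model, as baseline SDQ.

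Other places bear on the covariate:

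- The SAP trial design table has a row headed "Baseline for secondary outcome" that lists each scale. The outcome timing table and the list of baseline data confirm that these scales are measured before randomisation.
- SAP, Timing, units and derivation of secondaries, says for most scales that the baseline and 6-month data enter the main secondary analysis. It does not say how the baseline enters.
- Protocol, Analysis of primary and secondary outcomes, analyses adolescent self-report outcomes by linear regression "controlling for baseline scores, age, sex, and local authority". For parent-report secondary outcomes it says only that they are handled in a similar way to the primary.
- Protocol, Longitudinal follow-ups, adjusts for baseline measures.
- SAP, Mediation analyses, keeps SDQ_BL when the dependent variable becomes the mediator. No baseline mediator appears.

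**The concern.** A scale's own baseline is usually its best single predictor at follow-up. If a Kessler 6 or DAS-7 comparison is adjusted for the adolescent's baseline SDQ instead, chance differences between arms in baseline Kessler 6 or DAS-7 stay largely in the estimate, and the confidence interval is wider than it need be. The secondary outcomes are also tested under a Holm correction, so power given away here is hard to recover. Finally, two analysts working from this SAP could fit different models to the same scale, one with SDQ_BL and one with the own baseline. A SAP should rule that out before the data are seen.

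**Working it through.** **Inputs from the documents** (SAP, Sample size): "an effect size to be detected of 0.35 with 90% power and a two-sided alpha of 0.05"; "an average cluster size within families of up to a maximum of 1.5 parents"; "so also allow for an ICC=0.5"; baseline to follow-up correlation 0.5 for the primary outcome; 20% of families lost; 1:1 allocation.

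**Reproducing the plan's N.** A two-sample t-test for d = 0.35 needs 173 per arm.

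- Design effect: 1 + (1.5 − 1) × 0.5 = 1.25
- ANCOVA factor: 1 − 0.5² = 0.75
- 173 × 1.25 × 0.75 = 162.2 parents per arm
- 162.2 / 1.5 = 108.1, so 109 families
- 109 / 0.8 = 136.3, so 137 families per arm
- 137 × 1.5 = 205.5, so 206 parents per arm and 412 in total, as stated

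The plan's own arithmetic therefore relies on the (1 − r²) reduction from an outcome's own baseline.

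**Inputs that are assumed.** The documents give neither r, the correlation of a secondary scale with its own baseline, nor s, its correlation with baseline SDQ. I take r = 0.5 (borrowed from the primary outcome) and r = 0.7, each with s = 0.1 to 0.3.

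**Formulas.**

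- Residual variance with baseline SDQ relative to own baseline: (1 − s²) / (1 − r²). The SE ratio is its square root.
- Power at this trial's size, for a parent-report scale: 412 × 0.8 / 2 = 164.8 parents per arm, or 164.8 / 1.25 = 131.84 effective. Power = Φ(0.35 / (√(1 − ρ²) × √(2/131.84)) − 1.96), where ρ is the correlation with whichever baseline is in the model.

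| r | s | Variance ratio | SE ratio | Power, own baseline | Power, baseline SDQ |
|---|---|---|---|---|---|
| 0.5 | 0.1 | 0.99/0.75 = 1.32 | 1.15 | 0.907 | 0.815 |
| 0.5 | 0.3 | 0.91/0.75 = 1.21 | 1.10 | 0.907 | 0.846 |
| 0.5 | 0.5 | 0.75/0.75 = 1.00 | 1.00 | 0.907 | 0.907 |
| 0.7 | 0.1 | 0.99/0.51 = 1.94 | 1.39 | 0.978 | 0.815 |
| 0.7 | 0.3 | 0.91/0.51 = 1.78 | 1.34 | 0.978 | 0.846 |

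**Starting from exactly 90% power with the own baseline, r = 0.5.** The standardised effect is 1.96 + 1.2815 = 3.2415.

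- s = 0.1: Φ(3.2415/1.149 − 1.96) = Φ(0.86) = 0.81
- s = 0.3: Φ(3.2415/1.102 − 1.96) = Φ(0.98) = 0.84

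These figures use unadjusted alpha 0.05; under Holm both models have less power. The variance and SE ratios apply to adolescent-report scales as well. The power columns do not, because they use the parent design effect.

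**The case against.** The strongest reply is that SDQ_BL in the secondary equation is a leftover symbol. The SAP also defines the outcome Y as SDQ and reuses it without redefinition, so a fully literal reading would make SDQ the outcome of a Kessler 6 model. The derivation section says each scale's baseline data are used. The missing-data section speaks of outcomes and their respective control variables. The adherence model has a generic baseline term. All this makes own-baseline adjustment the likely intention, and that part of the reply stands. It does not settle the matter, because none of these places names the covariate or overrides the printed model. The SAP's allowance for covariates when a large imbalance is noted does not help either, since that choice follows sight of the data.

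A reader might infer that every secondary outcome is affected. The documents do not support this. Internalising, prosocial, peer and adolescent-report externalising scores are SDQ scores, for which baseline SDQ can mean the matching subscale. For out-of-home placement, the edge-of-care definition requires that the young person has not entered care, so an own baseline would carry little information.

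A reader might also infer a direct conflict with the protocol for all these scales. The protocol is explicit only for adolescent self-report outcomes and for the longitudinal model. For parent-report scales, own-baseline adjustment is implied.

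**Conclusion.** The point holds as a specification gap with a cost in precision, confined to the non-SDQ scales. Under randomisation the linear-model estimates remain unbiased, and the primary analysis is untouched.

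The size is conditional on correlations that the plan does not report. At r = 0.5 and s = 0.1 to 0.3, SEs are about 10 to 15% wider and 90% power becomes about 81 to 84%. At r = 0.7, SEs are about 34 to 39% wider; for d = 0.35 and s = 0.3, power is about 0.98 with the own baseline and 0.85 with baseline SDQ. If s equals r, nothing is lost.

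Two stronger readings should be avoided. A precision loss of a fifth to almost a half is not an established property of this plan: at r = 0.5 the loss in inverse variance cannot exceed 1 − 0.75 = 25%, and the upper end needs r near 0.7. Nor does power fall into the 60s at r = 0.7. That result would require own-baseline power to be reset to 90% at r = 0.7, which means a smaller effect than the design's (0.35 × 3.2415/3.979 = 0.285). With N fixed and d = 0.35, power under SDQ adjustment depends on s alone, and is 0.815 to 0.846 for s = 0.1 to 0.3.

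**What to change.** In SAP, Secondary outcomes analysis, replace SDQ_BL with the baseline value of the outcome being modelled, from the same respondent, and define the symbol there. For SDQ-based secondary outcomes, specify the matching subscale and respondent. State that out-of-home placement has no own-baseline term.

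In SAP, Mediation analyses, add the baseline mediator to both the mediator model and the outcome model, and keep SDQ_BL. It should not be replaced there, because baseline SDQ is a pre-randomisation confounder of the link between mediator and SDQ outcome.

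The cost is SAP wording only: the baselines are already scheduled and no extra data are needed. The change should be made before unblinded data are seen.

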- Parenting scale Adolescent: Baseline, 6-month and 12 month follow up data will be collected. Baseline and 6-month follow up data will only be used in the main secondary analysis, but will be repeated in the 12 month followup addendum report. The PSA is a 30 item measure with each item scored on a 7 point scale. A total score is created by summing all items, with low scores indicating good parenting and high scores indicating dysfunctional parenting.
- Dyadic Adjustment Scale (DAS-7): Baseline, 6-month and 12 month follow up data will be collected. Baseline and 6-month follow up data will only be used in the main secondary analysis, but will be repeated in the 12 month followup addendum report. The DAS-7 is comprised of varying response scales, including both ordinal and Likert scales.
 - Items 1–3 use a 6-point ordinal scale (from 5 = ‘Always Agree’ to 0 = ‘Always Disagree’).
 - Items 4–6 also use a 6-point ordinal scale (from 0 = ‘Never’ to 5 = ‘More Often’).
 - Item 7 is rated on a 7-point Likert scale (from 0 = ‘Extremely Unhappy’ to 6 = ‘Perfect’)

The total score for the DAS-7 is the sum of the responses to the seven items. The resultant score ranges from 0 to 36, with a higher score indicating more positive relationship quality. Scores less than 21 are considered to indicate a relationship in distress.

- Parent mental health – the Kessler 6 (K6) : Baseline, 6-month and 12 month follow up data will be collected. Baseline and 6-month follow up data will only be used in the main secondary analysis, but will be repeated in the 12 month followup addendum report. The K6 is scored using a 5-level response scale, ranging from 0 to 4 (0 = none of the time, 1 = a little of the time, 2 = some of the time, 3 = most of the time, 4 = all of the time); this generates a scoring scale with a range of 0 to 24.
- Parent Wellbeing - The Warwick-Edinburgh Mental Well-being Scale (SWEMWBS) - short version: Baseline, 6-month and 12 month follow up data will be collected. Baseline and 6-month follow up data will only be used in the main secondary analysis, but will be repeated in the 12 month followup addendum report. The SWEMWBS is scored by first summing the scores for each of the seven items, which are scored from 1 to 5. The total raw scores are then transformed into metric scores using the SWEMWBS conversion table which can be found here: https://warwick.ac.uk/fac/sci/med/research/platform/wemwbs/using/howto/swemwbs_raw_score_to_metric_score_conversion_table.pdf

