Following creation of the imputed datasets, the corresponding total scores will be calculated using the imputed item level data. All imputed datasets will then fit the primary and secondary models and pool estimates following Rubin's rules (Rubin, 2004; van Buuren, 2018).

Primary outcome

Given that each item is an ordered category, we will use an ordinal regression within the imputation model for each item.

Secondary outcome Similarly, the correct link function will be used according to the item's structure for each of the secondary outcomes, i.e. binary or ordered categorical accordingly. Therefore, a logistic or ordinal model will be used in the imputation for these items.

Additional analyses

Longitudinal followup analyses (12 month only) – Primary outcome

We will fit linear mixed models, accounting for repeated post-randomisation measures (6- and 12-months post-randomisation) within participants, adjusting for local authority to investigate the overall effect of the intervention on post-randomisation measures.

$$L1: Y_{ijk} = \beta_{0jk} + \beta_{1jk}time_{ijk} + r_{ijk}, \quad r_{ijk} \sim N(0, \sigma^2_{|X})$$

$$L2: \beta_{0jk} = \gamma_{00k} + \mu_{0jk}, \quad \mu_{0jk} \sim N(0, \tau_2^2)$$

$$\beta_{1jk} = \gamma_{100} + \mu_{1jk}, \quad \mu_{1jk} \sim N(0, \tau_2^2)$$

$$L3: \gamma_{00k} = \delta_{000} + \delta_{001}local_authority_k + \delta_{001}TX_k + \varsigma_{0k}, \quad \varsigma_{0k} \sim N(0, \tau_3^2)$$

Longitudinal followup analyses (12 month only) - Secondary outcomes

Secondary outcomes will be analysed similarly, but

$$L1: g(Y_{ijk}) = \beta_{0jk} + \beta_{1jk}time_{ijk} + r_{ijk}, \quad r_{ijk} \sim N(0, \sigma^2_{|X})$$

$$L2: \beta_{0jk} = \gamma_{00k} + \mu_{0jk}, \quad \mu_{0jk} \sim N(0, \tau_2^2)$$

$$\beta_{1jk} = \gamma_{100} + \mu_{1jk}, \quad \mu_{1jk} \sim N(0, \tau_2^2)$$

$$L3: \gamma_{00k} = \delta_{000} + \delta_{001}local_authority_k + \delta_{001}TX_k + \varsigma_{0k}, \quad \varsigma_{0k} \sim N(0, \tau_3^2)$$

For the remaining secondary outcomes, their effect sizes will be reported as either Hedges' g (same as primary outcome) or rate ratios (other secondary outcomes, exponentiated parameter estimates), given that generalized linear mixed effects models with log link function are used to model the data and that the measures are positively scored integers with some amount of skew anticipated (Barnett and Dobson, 2008).

Mediation analyses (12 months report only)

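### The SAP endorses Poisson models for bounded questionnaire scores on a ground that does not support them; if used, they could give standard errors that are too large for under-dispersed secondary outcomes

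*SAP*

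**What the plan says.** SAP, Secondary outcomes analysis: these outcomes follow the primary method, a linear mixed model with a family random intercept. If a score shows range restriction, a generalised linear mixed model will be considered, Poisson for scores and logistic for out-of-home placement. Because scores are positive integers, "so the Poisson distribution under this condition is completely acceptable if needed". The equation printed there has a family intercept and also a level-1 normal term, r_ik.

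SAP, Alternative methods if distributional assumptions not met: a generalised mixed model is preferred to transformation. The checks listed under Assumption checking are linearity, homogeneity of variance and normality of residuals. There is no dispersion check.

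SAP, Longitudinal followup analyses (secondary outcomes, 12 months): effects will be Hedges' g or rate ratios, "given that generalized linear mixed effects models with log link function are used to model the data".

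SAP, Timing, units and derivation of secondaries: the ranges include 0-10 (prosocial, peer), 0-20 (internalising, externalising), 0-20 (CBQ-20), 0-24 (Kessler 6), 0-36 (DAS-7), 7-35 (closeness) and 0-165 (SRDM).

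Protocol, Analysis of primary and secondary outcomes: adolescent self-report outcomes use linear regression. "No random effects are included when analysing these outcomes".

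**The concern.** A score can be a non-negative integer and still have a variance far from its mean. A Poisson model takes its standard errors from the mean, so they are wrong whenever the residual variance differs from it. The trigger makes this worse: range restriction means that a bound is active, and Poisson has no upper bound. On a short scale with scores towards the top, the variance tends to be small and the mean large, so the Poisson standard error is too big.

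At stake are the secondary P values and intervals. The P values enter the Holm procedure, so an inflated one can hide a real effect and leave the next outcome with a stricter threshold. Rate ratios are also hard to interpret for a bounded rating scale.

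**Working it through.** **The plan's own figure.** The SAP's inputs are "an effect size to be detected of 0.35 with 90% power and a two-sided alpha of 0.05", "an average cluster size within families of up to a maximum of 1.5 parents", ICC 0.5, baseline correlation 0.5 and 20% loss. Two-sample t-test: 172.5 per arm. Then 172.5 × (1 − 0.5²) × [1 + (1.5 − 1) × 0.5] / (1 − 0.20) = 172.5 × 0.75 × 1.25 / 0.8 = 202.1, so 203 per arm and 406 in total. This is within 3% of the stated 412. Families followed up: 275 × 0.8 = 220. The documents give no mean, SD, dispersion or power for any secondary outcome, so those below are assumptions.

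**Approximate size.** With one respondent per family and no random effect,

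Poisson SE / true SE ≈ √(mean / residual variance), with residual variance = SD² × (1 − 0.5²).

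- 0-10 scale, mean 6.5, SD 2: residual variance 4 × 0.75 = 3, and √(6.5/3) = 1.47.
- Parents, 110 families with two and 110 with one: Σn²/Σn = (440 + 110)/330 = 1.67, design effect 1 + 0.67 × 0.5 = 1.33, ratio 1.47/√1.33 = 1.27.
- Closeness, mean 25, SD 4: √(25/12) = 1.44, and 1.44/√1.33 = 1.25 for parents.
- The ratio without clustering is 1 at SD = √(mean/0.75): 2.9 (0-10, mean 6.5), 5.8 (7-35, mean 25), 5.3 (0-36, mean 21) and 3.5 (0-24, mean 9). Below these SDs Poisson errors are too large.

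**Simulation.** 500 null trials per scenario, 220 families, ICC 0.5, r = 0.5, scores rounded and clipped to the stated range. Cells show model SE / true SE and type I error. The simulation error of the ratio is about 3%.

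| Assumed outcome | Poisson, no random effect | Poisson with family intercept | Linear, cluster-robust SE |
|---|---|---|---|
| 0-10, parent, mean 6.5, SD 2 | 1.28, 1.6% | 1.28, 1.4% | 0.98, 6.2% |
| 0-10, adolescent, mean 6.5, SD 2 | 1.45, 0.0% | 1.45, 0.0% | 0.97, 4.4% |
| Closeness, mean 25, SD 4 | 1.27, 2.0% | 1.27, 2.0% | 1.02, 4.4% |
| Closeness, mean 25, SD 6 | 0.92, 7.0% | 1.06, 4.0% | 1.07, 4.2% |
| DAS-7, mean 21, SD 6 | 0.79, 13.2% | 1.02, 6.2% | 1.03, 5.4% |
| Kessler 6, mean 9, SD 5.5 | 0.58, 23.6% | 1.02, 5.8% | 1.02, 6.0% |
| Self-regulation, mean 60, SD 12 | 0.66, 19.8% | 1.00, 5.2% | 1.00, 4.6% |
| Adolescent externalising, mean 10, SD 5.7 | 0.68, 19.0% | 0.97, 6.0% | 1.00, 4.0% |
| SRDM, skewed, mean 15 | 0.25, 61.8% | 1.05, 4.2% | 1.06, 3.4% |

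In the under-dispersed rows the family intercept is estimated at about zero. Adding r_ik left every parent-report ratio unchanged; with one adolescent per family the intercept already plays that part. A second set of simulated scores (0-10 scale, mean 7, SD 2.2) gave standard errors 37% too large without a random effect and 22% too large for parents with a family intercept. Poisson with cluster-robust standard errors also held in all nine rows: across Poisson and linear, ratios were 0.97-1.07 and type I error 3.4-6.4%.

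**Power.** A test with 90% power has expected z = 1.96 + 1.28 = 3.24. An SE ratio of 1.28 moves the effective cut-off to 1.96 × 1.28 = 2.51, so power is Φ(0.73) = 77%. A ratio of 1.45 gives 1.96 × 1.45 = 2.84, so power is Φ(0.40) = 66%.

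**The case against.** The linear mixed model is the default, and at 6 months Poisson is only to be considered. This stands, so the harm is conditional. But no threshold for range restriction is given, and no listed check would reveal a wrong dispersion.

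A reader might infer false positives as well. The SAP equates 0.35 SD with about 2 points, so SD = 2/0.35 = 5.71 and residual variance = 32.7 × 0.75 = 24.5, above any possible mean on a 0-20 scale. A Poisson model without a random effect would then be anti-conservative (19% in the table). The documents do not support that reading: the protocol's absence of random effects belongs to a linear regression, its GLM fallback names no Poisson, and the SAP's Poisson carries random effects, which absorb the excess. Only a combination of the protocol's structure with the SAP's distribution would produce it. The SD is also derived for parent report.

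The SAP drops to linear regression with cluster-robust errors if random-effect variance is insufficient, and the under-dispersed cases would meet that description. But the rule is written for the primary linear model, and its extension to a Poisson mixed model is only arguable.

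The 12-month text might be read as making Poisson the standing model. It names a log link, not Poisson, and also allows Hedges' g, so it needs clarifying and proves no more.

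For wellbeing, "The total raw scores are then transformed into metric scores using the SWEMWBS conversion table". Whether converted scores are still integers depends on a table outside the documents, so this cannot be counted against the plan.

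**Conclusion.** The justification for Poisson is unsound, and acting on it could make secondary standard errors too large on under-dispersed bounded scales: about 22-28% for parent report and up to about 45% with one adolescent per family. The error is conservative; it costs power and does not create false findings. The sizes depend on assumed means and SDs, r = 0.5 and ICC 0.5, and shrink or vanish as the SD approaches the break-even values above. The 90% power is a benchmark, since only the primary outcome is powered. Under the SAP's mixed model the five clearly over-dispersed scenarios held at 4.2-6.2%, so a claim of errors in both directions goes too far. The primary analysis, which the SAP keeps on the identity link, is unaffected.

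**What to change.** 1. Delete the sentence endorsing Poisson for positive integer scores.
2. Keep the linear (mixed) model as default for all bounded questionnaire scores at 6 and 12 months, with robust standard errors, clustered by family for parents. Logistic regression for out-of-home placement stays as planned.
3. If a log-link model is used for any score, check dispersion and use robust standard errors.
4. Use a negative binomial model with robust standard errors for the SRDM frequency score.
5. Reconcile the 12-month log-link wording with the 6-month rule, and the protocol with the SAP on the model and random effects for adolescent report.

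The cost is SAP wording and minor programming. The downside is that bounded scores are summarised by a mean difference and not a ratio. Robust errors with a Poisson model also performed well, so the linear default is chosen for interpretability as much as for error control.
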